### 3.2.2.1 Premedication for Obinutuzumab

Detailed guidance for the optimal pretreatment regimen is provided below ([Table 14](#)).

**Table 14: Premedication recommendations for obinutuzumab**

| Day of treatment cycle  | Patients requiring premedication | Premedication                            | Administration  |
|---|----------------------------------|--|---|
| Cycle 1, Days 1 and 2 (Dose-finding, Arms 1 and 2)
Cycle -2, Days 1 and 2 (Dose expansion, Arms 3 and 4) | All patients                     | Intravenous corticosteroid   | Administered 30-60 minutes before obinutuzumab infusion |
|   |                                  | Acetaminophen 650 mg or equivalent NSAID |   |
|   |                                  | Anti-histaminic              |   |
| All subsequent infusions    | All patients                     | Acetaminophen 650 mg or equivalent NSAID | Administered 30-60 minutes before obinutuzumab infusion |
|   |                                  | Anti-histaminic              |   |

 100 mg prednisone/prednisolone or 20mg dexamethasone or 80mg methylprednisolone. Hydrocortisone should not be used as it has not been effective in reducing rates of IRR.

 For example: 25 or 50 mg diphenhydramine or equivalent

 Additional premedications may be given based on PI discretion and nature of previous infusion reactions

### 3.2.3 Venetoclax administration

Venetoclax should be taken with a meal. If vomiting occurs within 15 minutes after taking venetoclax and all expelled tablets are still intact, another dose may be given. Otherwise, no replacement dose is to be given. In cases where a dose of venetoclax is missed or forgotten, the patient should take the dose as soon as possible and ensure that the minimal interval between the current dose and the next dose is at least 16 hours in order to avoid excessive drug accumulation after the next dose.

Venetoclax will be dispensed to patients in bottles. All doses of venetoclax taken in the clinic or day hospital should be taken from the bottle dispensed to the subject. Unused venetoclax tablets dispensed during previous visits must be returned. Returned tablets must not be re-dispensed to anyone.

Patients will be encouraged to complete and return an optional drug diary as a memory aid to help document the date and time of all self-administered study drugs ([Appendix D](#)).

### **3.3 DOSE MODIFICATIONS**

The following sections detail dose modifications/delay guidelines for each individual drug of the window or triplet combination regimen based on documented toxicity. It is the responsibility of the investigator to determine the most likely agent responsible for the observed toxicity and follow dose modification/delay guidelines in the appropriate section listed below. Dose reductions or delay for multiple study agents based on the same toxicity is not necessary and dosing should be modified or delayed only for the most likely offending agent identified by the investigator.

Dose adjustments are to be made according to the system showing the greatest toxicity. If a patient experiences several toxicities and there are conflicting recommendations, the recommended dose adjustment that reduces the dose to the lowest level will be used.

Dose modifications of magrolimab and obinutuzumab are not allowed throughout the study treatment, only dose delays can be considered per investigator's discretion. If AEs occur that are related to either of these infusional agents, then dose delays of up to 2 weeks during the window period, and up to 4 weeks during the triplet therapy, are permitted until the investigator feels it is safe to resume. If, after the delay the investigator does not feel it is safe to re-initiate therapy with magrolimab or obinutuzumab, then the patient should be taken off study treatment.

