### 1.2.7 Combination Studies

#### 1.2.7.1 Obinutuzumab and Venetoclax in Patients with CLL

Venetoclax has been tested in combination with obinutuzumab in patients with previously untreated CLL and coexisting conditions(69). Obinutuzumab was administered for 6 cycles starting with 100 mg on day 1 and 900 mg on day 2 (or 1000 mg on day 1), 1000 mg on day 8 and 1000 mg on day 15 of cycle 1, and subsequently 1000 mg on day 1 of cycles 2 through 6. The daily oral venetoclax regimen was initiated on day 22 of cycle 1, starting with a 5-week dose ramp-up from 20 mg to 400 mg, thereafter continuing at 400 mg daily until completion of cycle 12(69). At least one adverse event of any grade occurred in 200/212 (94%) of patients. Adverse events leading to drug discontinuation occurred in 34/212 (16%) of the patients. The most common grade 3 or 4 adverse event was neutropenia. Grade 3 or 4 febrile neutropenia and grade 3 or 4 infections were reported in 11/212 (5.2%) and 35/212 (17.5%) of patients, respectively. Tumor lysis syndrome was reported in 3 patients (all cases occurred during treatment with obinutuzumab and before treatment with venetoclax); while 5 patients had fatal AEs during treatment with infection being the cause of death in 4 patients, and MDS in 1 patient.

**Table 6: Summary of AEs Occurring in  $\geq 10\%$ , and Grade 3/4 AEs in 212 CLL Patients Receiving Venetoclax and Obinutuzumab(69)**

|                               | All Grades
N (%) | Grade 3/4
N (%) |
|-------------------------------|---------------------|--------------------|
| Any                           | 200 (94)            | 167 (78)           |
| Neutropenia                   | 122 (58)            | 112 (53)           |
| Thrombocytopenia              | 51 (24)             | 29 (14)            |
| Anemia                        | 35 (17)             | 17 (8)             |
| IRR                           | 95 (45)             | 19 (9)             |
| Diarrhea                      | 59 (28)             | 9 (4.2)            |
| Nausea                        | 40 (19)             | 0 (0)              |
| Infections                    | Not reported        | 10 (4.7)           |
| Fatigue                       | 48 (23)             | 0 (0)              |
| Serious adverse events | 104 (49)     |                    |
| Pneumonia                     | 10 (5)              |                    |
| Sepsis                        | 6 (3)               |                    |

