#### **3.3.2 Modifications for Hematologic Toxicity**

Dose modifications for hematologic toxicities must be done according to the guidelines below ([Table 16](#)). The investigator may judge a more conservative dose modification if appropriate. Therefore, if these guidelines are not followed, the rationale for other measures is to be documented in detail in the patient's medical record. Use of growth factors (filgrastim, pegfilgrastim, etc.) and transfusion support is permitted per investigator's discretion.

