**Table 16: Dose modifications for hematologic toxicity**

| Event(s)   | Dose Delay or Modification   |
|--|--|
| CTCAE Grade 3 or 4 neutropenia, without infection or fever | During window period
Delay next magrolimab and obinutuzumab infusion until toxicity recovers to $\leq$ Grade 2. Upon recovery to $\leq$ Grade 2, resume previous doses of magrolimab and obinutuzumab. Dose delays of longer than 2 weeks are not permitted. |
| CTCAE Grade 3 or 4 thrombocytopenia                        | During triplet therapy after DLT assessment (Cycle 1, Arms 1 and 2)
Hold venetoclax and delay next magrolimab and obinutuzumab infusions until toxicity recovers to $\leq$ Grade 2.  |
| Febrile neutropenia a                           |  |
| CTCAE Grade 3 or 4 anemia                                  | If toxicity recovers to $\leq$ Grade 2, patient may be treated at one venetoclax dose level lower. b Dose delays of longer than 4 weeks are not permitted.  |

CTCAE = Common Terminology Criteria of Adverse Events;

- a. These patients should recover from neutropenia, without fever
- b. If subsequent treatment with venetoclax at lower dose levels does not result in recurrent Grade 3 or higher hematologic toxicity, the dose of venetoclax can be increased to the original dose level during later cycles.

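### Section 3.3 limits a delay to the one agent judged responsible, while Table 16 delays every infused drug and, in triplet therapy after DLT assessment, also holds venetoclax for the same cytopenia

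*Combined protocol and SAP*

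**What the plan says.** Section 3.3 (Dose Modifications) asks the investigator to identify the agent most likely to have caused a toxicity. It then says "Dose reductions or delay for multiple study agents based on the same toxicity is not necessary" and that "dosing should be modified or delayed only for the most likely offending agent identified by the investigator".

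Section 3.3.2 (Modifications for Hematologic Toxicity) says: "Dose modifications for hematologic toxicities must be done according to the guidelines below". It allows one named departure: "The investigator may judge a more conservative dose modification if appropriate". Any other departure needs a detailed rationale in the medical record.

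Table 16 lists four events: "CTCAE Grade 3 or 4 neutropenia, without infection or fever", Grade 3 or 4 thrombocytopenia, febrile neutropenia, and Grade 3 or 4 anemia. Its instructions depend on the treatment period:

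- **Window:** "Delay next magrolimab and obinutuzumab infusion until toxicity recovers to" Grade 2 or lower, with a 2-week limit.
- **Triplet therapy after DLT assessment:** "Hold venetoclax and delay next magrolimab and obinutuzumab infusions until toxicity recovers to" Grade 2 or lower, with a 4-week limit. On recovery, venetoclax may resume one dose level lower.

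Section 3.3.1.1 deals separately with Cycle 1 of Arms 1 and 2. Antibody delays are to be avoided there, and a DLT leads to all study therapy being held.

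**The concern.** The two rules give different instructions for one event. Section 3.3 makes the action depend on attribution and confines it to one drug. Table 16 has no attribution step and acts on every drug then being given.

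Two patients with the same Grade 3 cytopenia could therefore have different drugs withheld, with both investigators able to point to current text. Delivered dose of all three agents would then depend partly on which passage was used. So might the number of patients who reach the 2- or 4-week limit.

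Safety and tolerability are the primary endpoint, and the events concerned are expected ones. Section 1.2.7.1 says of venetoclax with obinutuzumab: "The most common grade 3 or 4 adverse event was neutropenia".

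**Working it through.** **1. The passages side by side**

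| Question | Section 3.3 | Section 3.3.2 and Table 16 |
|---|---|---|
| Is attribution required? | Yes, to the most likely agent | No |
| Window: what is delayed? | One agent | Both antibodies |
| Triplet after DLT assessment: what is held? | One agent | Venetoclax and both antibodies |
| Basis for delaying an antibody | Investigator discretion, for events related to an infused agent | The cytopenia itself |
| Force | Should, and only | Must, with documented departures |

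Example: a Grade 3 anemia in Cycle 4 is attributed to magrolimab. Section 1.2.4.1 describes loss of older red cells as an expected effect of that drug. Under Section 3.3 only magrolimab is delayed. Under Table 16 all three drugs stop, and venetoclax may restart one level lower.

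**2. Does any text settle it?**

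- The tie-break in Section 3.3 covers a patient with several toxicities whose recommendations differ. Here there is one toxicity and two rules.
- The only departure named in Section 3.3.2 is a more conservative one. Delaying one drug instead of three is less conservative, so an investigator who follows Section 3.3 must document a departure from Section 3.3.2.
- Section 3.3.1 is headed as exceptions, but covers only DLT evaluation. Section 3.3.2 carries no such label.
- Table 17 leaves multi-agent delay for Grade 3 non-hematologic events in triplet therapy to the investigator's discretion, so it can be read together with Section 3.3. Table 16 has no equivalent wording.

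**3. How often could it arise?**

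The protocol's own figure first. Table 6 gives Grade 3/4 neutropenia in 112 of 212 patients: 112/212 = 52.8%, which rounds to the stated 53%. In the same table Grade 3/4 thrombocytopenia is 29/212 = 13.7% and anemia 17/212 = 8.0%. These may overlap within patients, so they are not added.

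There are no triplet data. As an assumption, each cited Grade 3/4 neutropenia rate is applied to the 66 treated patients of Section 10.2 (24 dose-finding + 42 expansion). Expected number = rate × 66.

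| Source in the protocol | Rate | Expected of 66 |
|---|---|---|
| Venetoclax alone, NHL (1.2.5.1) | 11% | 7.3 |
| Venetoclax alone, CLL (Table 1) | 41% | 27.1 |
| Venetoclax-obinutuzumab, untreated CLL (Table 6) | 53% | 35.0 |
| Venetoclax-lenalidomide-obinutuzumab, NHL (1.2.7.2) | 91% | 60.1 |

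The total of 66 assumes that both dose-finding cohorts de-escalate. If neither does, 12 + 42 = 54 patients are treated, and the range becomes 0.11 × 54 = 5.9 to 0.91 × 54 = 49.1.

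Some events would occur only in Cycle 1 of Arms 1 and 2, where this part of Table 16 does not apply. The documents do not allow that share to be estimated, so the counts are upper figures for each rate.

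**The case against.** The strongest reply is that the specific rule governs the general one. Section 3.3 sends the reader to the appropriate section below it, and for cytopenias that is 3.3.2. Sections 3.4.2.4 and 12.3.1 also send neutropenia there. Most sites would probably follow Table 16. The mandatory wording is softened too, because departures are allowed with a documented reason. This makes Table 16 the likelier practice, but it does not remove the conflict: no text gives it priority, and the word *only* in Section 3.3 is not permissive.

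A second objection concerns the table. Its row layout was broken in extraction from the PDF, and applying the instructions to all four events assumes a merged cell. That is plausible, but it should be checked against the formatted page.

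Three stronger readings are tempting and not supported:

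- **That the most common toxicity of this regimen is affected, in about 35 of 66 patients.** That count carries over one rate from previously untreated CLL patients with coexisting conditions. Elsewhere in the protocol, infusion reactions lead for obinutuzumab alone in indolent NHL, and anemia heads the magrolimab list.
- **That the 25% stopping rule is distorted.** Section 10.2 counts patients who could not complete therapy because of toxicity, not holds. The 4-week triplet limit is the same in Section 3.3 and Table 16. Nothing shows how often holding one drug rather than three would change who exceeds it.
- **That tolerability becomes uninterpretable.** The primary-endpoint analysis in Section 10.4.2 reports DLTs to the triplet. These are assessed in Cycle 1 of Arms 1 and 2, where Section 3.3.1.1 applies.

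**Conclusion.** The contradiction stands in current text and is wrong as written, within limits. It covers the window, where the choice is between one antibody and both, and triplet therapy after DLT assessment, where it is between one drug and all three. It does not cover Cycle 1 of Arms 1 and 2.

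The consequence that follows directly is inconsistent delivered dose. An effect on how often the delay limits are reached is possible, in an unknown direction and of unknown size. An effect on the 25% rule is possible but not shown.

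The number of patients exposed is very uncertain: about 7 to 60 of 66, on the assumption that cited neutropenia rates carry over to an untested triplet and before removing events in the excluded period. The conclusion also rests on Table 16's instructions covering all four listed events. The contradiction itself does not depend on the patient count.

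**What to change.** Reconcile the passages. Add a sentence to Section 3.3 stating how its single-agent rule relates to Table 16, separately for the window and for triplet therapy after DLT assessment, and use matching words in Section 3.3.2. Which rule applies is a clinical decision for the investigators; the text should give one answer.

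Record for each hold or delay which agents were held, so that delivered dose and reasons for discontinuation can be described by drug.

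The cost is a sentence or two and one data item, within an amendment that needs IRB approval. Sample size and planned analyses do not change.

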#### **3.3.1 Exceptions to Dose Modifications/Delays during DLT Evaluation Windows**

##### **3.3.1.1 During venetoclax dose-finding (addition of venetoclax to magrolimab and obinutuzumab)**

Dose delays of magrolimab and obinutuzumab should be avoided during the DLT assessment (i.e., Cycle 1 of triplet combination therapy in Arms 1 and 2) to allow for identification of toxicities. If a patient experiences a DLT to triplet combination therapy, then all study therapy should be held for up to 2 weeks per the investigator. If DLT resolves and it is deemed safe to re-initiate therapy, then magrolimab and obinutuzumab should be re-started at the prior dose, and venetoclax should be re-started at one dose level lower. Dose levels for venetoclax dose modifications are mentioned in the table below ([Table 15](#)).

**Table 15: Venetoclax dose levels for dose-modifications**

| Dose level | Cohorts 1,3
(FL) | Cohorts 2, 4, 5, 6
(MZL, MCL, CLL) |
|-------------------|-----------------------------|---|
| DL-3       | 200 mg                      | 50 mg   |
| DL-2       | 400 mg                      | 100 mg  |
| DL-1       | 600 mg                      | 200 mg  |
| DL1        | 800 mg                      | 400 mg  |

#### **3.3.2 Modifications for Hematologic Toxicity**

Dose modifications for hematologic toxicities must be done according to the guidelines below ([Table 16](#)). The investigator may judge a more conservative dose modification if appropriate. Therefore, if these guidelines are not followed, the rationale for other measures is to be documented in detail in the patient's medical record. Use of growth factors (filgrastim, pegfilgrastim, etc.) and transfusion support is permitted per investigator's discretion.

**Table 16: Dose modifications for hematologic toxicity**

| Event(s)   | Dose Delay or Modification   |
|--|--|
| CTCAE Grade 3 or 4 neutropenia, without infection or fever | During window period
Delay next magrolimab and obinutuzumab infusion until toxicity recovers to $\leq$ Grade 2. Upon recovery to $\leq$ Grade 2, resume previous doses of magrolimab and obinutuzumab. Dose delays of longer than 2 weeks are not permitted. |
| CTCAE Grade 3 or 4 thrombocytopenia                        | During triplet therapy after DLT assessment (Cycle 1, Arms 1 and 2)
Hold venetoclax and delay next magrolimab and obinutuzumab infusions until toxicity recovers to $\leq$ Grade 2.  |
| Febrile neutropenia a                           |  |
| CTCAE Grade 3 or 4 anemia                                  | If toxicity recovers to $\leq$ Grade 2, patient may be treated at one venetoclax dose level lower. b Dose delays of longer than 4 weeks are not permitted.  |

CTCAE = Common Terminology Criteria of Adverse Events;

- a. These patients should recover from neutropenia, without fever
- b. If subsequent treatment with venetoclax at lower dose levels does not result in recurrent Grade 3 or higher hematologic toxicity, the dose of venetoclax can be increased to the original dose level during later cycles.

### **3.3.3 Modifications for Non-hematologic Toxicity (for all toxicities except as specified below)**

Dose modifications for non-hematologic toxicities are outlined below ([Table 17](#)). The investigator may judge a more conservative dose modification appropriate; therefore, if these guidelines are not followed, the rationale for other measures is to be documented in detail in the patient's medical record.

**Table 17: Dose modifications for non-hematologic toxicity**

| Event(s)                                | Dose Delay or Modification   |
|---|--|
| Grade 1-2 a                  | No dose reduction or delay is necessary. Symptomatic management per investigator's discretion.   |
| Grade 3 a                    | 
During window period
 
Delay next magrolimab and/or obinutuzumab infusion for a maximum of 2 weeks. If improvement to Grade <math>\leq 2</math> or baseline, resume previous doses of magrolimab and obinutuzumab. Dose delays of longer than 2 weeks are not permitted.
 
During triplet therapy after DLT assessment (Cycle 1, Arms 1 and 2)
 
Per investigator's discretion, venetoclax, magrolimab and obinutuzumab can be delayed for a maximum of 4 weeks.
 
First episode: If improvement to Grade <math>\leq 2</math> or baseline, resume previous doses of venetoclax, magrolimab and/or obinutuzumab.
 
For subsequent episodes: If improvement to Grade <math>\leq 2</math> or baseline, venetoclax can be restarted at one dose level lower.b
 
<math>\geq 3</math> episodes: Consider permanent discontinuation of the offending agent. Permanent discontinuation of all study treatment may be considered per investigator's discretion.
 |
| Grade 4 a                    | Permanently discontinue all study treatment  |
| Toxicity requiring delay for $>4$ weeks | Permanently discontinue all study treatment  |

### 3.3.4 Infusion Reactions to Magrolimab

Infusion-related reactions are defined by the NCI CTCAE Version 5.0 under “Injury, poisoning and procedural complications” as follows: “a disorder characterized by adverse reaction to the infusion of pharmacological or biological substances.” The time frame for infusion reaction assessment is the 24-hour period beginning from the start of the magrolimab infusion. Re-challenge of patients has not resulted in worsening of any adverse reaction and patients who continue on therapy following an initial infusion reaction have tolerated subsequent treatments without incident. There have been no late hypersensitivity reactions.

#### 3.3.4.1 Grade 1

For Grade 1 symptoms (mild transient reaction; infusion interruption not indicated; intervention not indicated):

- Monitor patient until recovery from symptoms.

- Patients who experience IRRs with the first 2 doses of magrolimab should continue premedication with corticosteroids prior to subsequent doses at the Principal Investigator's discretion.

### 3.3.4.2 Grade 2

For Grade 2 IRR, described as requiring symptomatic treatment and prophylactic medications (e.g. antihistamines, non-steroidal anti-inflammatory drugs, narcotics, corticosteroids, IV fluids) for  $\leq$  24 hours, infusion interruption is indicated:

- Stop the magrolimab infusion, begin an IV infusion of normal saline, and treat the patient with diphenhydramine 50 mg IV (or equivalent) and/or 500 to 750 mg oral paracetamol/acetaminophen.
- Monitor patient until resolution of symptoms.
- Corticosteroid therapy may also be administered.
- If the infusion is interrupted, wait until symptoms resolve, then restart the infusion at 50% of the original infusion rate when symptoms resolve.
- If no further complications ensue after 60 minutes, the rate may be increased to 100% of the original infusion rate. Monitor the patient closely.
- If symptoms recur, then stop infusion and disconnect the patient from the infusion apparatus; no further magrolimab will be administered at that visit.
- Patients who experience IRR with the first 2 doses of magrolimab should continue premedication with corticosteroids prior to subsequent doses at the Principal Investigator's discretion.
- Patients who experience an infusion reaction of Grade 2 during the 4-hour post-infusion observation period that does not resolve during that time should be observed for 24 hours or until the adverse event resolves, with vital sign measurements every 4 hours and additional evaluations as medically indicated for the management of the adverse event.

### 3.3.4.3 Grade 3 or 4

For Grade 3 IRR described as prolonged reactions or recurrence of symptoms following initial improvement, or where hospitalization indicated for other clinical sequelae (e.g., renal impairment, pulmonary infiltrates), or Grade 4 IRR described as having life-threatening consequences, where urgent intervention is indicated:

- Immediately discontinue infusion of magrolimab.
- Begin an IV infusion of normal saline. Systemic steroids, bronchodilators and/or epinephrine may be used as per institutional guidelines.
- The patient should be monitored until the investigator is comfortable that the symptoms will not recur.
- Patients who have Grade 3 infusion reactions with the first dose can be offered the opportunity to stay on study and must be given premedication prior to subsequent doses. In this setting, premedication with acetaminophen (650 mg PO), diphenhydramine (25-50 mg PO or IV) and dexamethasone (4-20 mg IV), or a comparable regimen, is recommended for the subsequent 2 doses. Long-term premedication can be discontinued if clinically indicated, for example if the patient does not demonstrate further infusion reactions after multiple doses.

- In patients who receive premedication and still experience a recurrent Grade 3 infusion reaction, or patients who experience a Grade 4 IRR at any time should be permanently discontinued from the study treatment.
- All patients with Grade 3 or greater infusion related reactions will be observed for an additional 24 hours or longer until the adverse event resolves, with vital sign measurements every 4 hours and additional evaluations as medically indicated for the management of the AE.
- In the case of late-occurring hypersensitivity symptoms (e.g., appearance of localized or generalized pruritus after Day 1 but within 1 week after treatment), symptomatic treatment may be given (e.g., oral antihistamine or corticosteroids).

